For all participants, the following attributes will be measured at recruitment to *characterize* the sample: i) child's sex/gender and age, ii) postal code and parents' education (SES, urban/rural), iii) child's developmental and independence score using the Vineland [11] (phone interview), iv) family context (Parenting Stress Index [12], v) developmental services used. Finally, at baseline, families will be contacted by phone and asked a three question screening survey to assess their "readiness" to benefit from the coaching intervention:(1) do you feel that you have been provided with sufficient information about your child's health and development? (no = 1 point); (2) are there things that you would like to change about how your child is accessing support or services in support of their development? (yes = 1 point); (3) Can you give an example of how you or health providers could help YOU change things for the better with respect to your child's development? (yes = 1 point). In addition, at baseline, care and social support networks will be documented in both arms of the study.

Because this is a pragmatic trial that is meant to be generalized to the real-world context, blinding is not appropriate or possible. In addition, the outcome measures to be used are primarily self-report in nature, again replicating what would be cost-effective and patient oriented in the real-world setting. Outcome measures will be measured at baseline, 8 months post-entry and 12 months post-entry.

The initial primary outcome (Hypothesis 1) relates to the assessment of feasibility and initial acceptability of the protocol implementation. Protocol feasibility will be evaluated with respect to ability to recruit and implement a standardized approach to coaching and use of the platform across the four diverse sites. The feasibility and acceptability of the intervention will be evaluated by: percent of successful virtual visits with the coach (defined as the ability to connect with family at home via telephone or e-health tool); participants' utilization of Igloo-based online education; parental (mother AND father, if both involved, or other caregiver, as appropriate) satisfaction surveys; and, feedback from the coaches.

Once past the feasibility stage, outcomes will be measured at 8 months and 12 months after recruitment. The primary outcome of interest in the RCT is the *parents' ability to self-manage and promote their child's development*. Thus, the primary outcome measure is the Family Empowerment Scale, which focuses on empowerment at the family (managing the day to day), services (working with system to receive adequate services) and community (finding or advocating for needed supports, policies, agencies) levels [13]. Its psychometric properties are acceptable. A second measure will be the Parents' Sense of Competence Scale which measures satisfaction (anxiety, motivation, frustration) and efficacy (capability, problem-solving) with parental roles [14].

Secondary measures of intervention efficacy apply the Triple Aim Framework and will include:

1. Parental well-being: SF-36 [15] (quality of life) and the Parenting Stress Index [12] (parent stress level).
2. Family health care experience: Measure of Process of Care [16] (the extent to which care is family-centred)

3. Health care costs/ service utilization patterns: the Resource Utilization Questionnaire (adapted from Drs. [name] and [name]) uses standardized metrics for the evaluation of costs (health care and out-of-pocket), consequences and benefits from the patient, provider and health system perspectives.
4. Care and social networks: Care and social networks will be tracked using Igloo analytics. This will include tracking during the transition from preschool to school-aged services and the identification of professional and community supports.
5. Engagement of mothers and fathers with BRIGHT program: Analysis of electronic contact data from Igloo platform by mothers and fathers (gender).

Exploratory measures will include:

Child's functional abilities and independence: Vineland – daily living skills, socialization, etc .. Importantly, in the spring of 2017, an online “needs assessment” survey was conducted with Canadian families to influence the content of the coach intervention and to determine the outcomes of greatest interest to families and administrators.

Additional Qualitative study regarding acceptability of the BRIGHT program: At study completion, to better appreciate the patients/families' experience with the BRIGHT model, we will conduct exit interviews on those in the intervention group. Key ingredients to the intervention (what they most appreciated/valued) and the factors that influenced (positively and negatively) the success of the intervention will be probed. The responses will be coded using qualitative analysis software and analysis will be conducted to determine major themes. In addition, exit interviews with the coaches will similarly be completed to determine the feasibility of the intervention from their perspective.

Data collection and management:

Each of the four sites will have a part-time RA, with a Study Coordinator at the Montreal site. The Coordinator will organize regular teleconferences with the RAs to trouble shoot any challenges in recruitment or data collection, and will ensure standardization of procedures. There will be a data sharing agreement signed by the four sites, with a common REDCap database for all to use for data entry. The password-protected database will have personal information de-identified and a separate list will be kept of participants (child, parents) names, birth date of the child, and address/email. The Study Coordinator will have oversight of the database and ensure that there are no missing values.

Timeline:

Year 1: Develop coach manual and training; develop online educational tools and customize Igloo platform.
Year 2: Pilot study; finalize methods and measures; begin recruitment. *Year 3:* Complete recruitment; 8 month outcome evaluation for early participants. *Year 4:* Complete 12 month intervention and outcomes. *Year 5:* statistical analyses; qualitative interview analysis; manuscript preparation; KT plan to include policy brief.

Statistical analyses:

Descriptive statistics will be used to characterize our sample in the experimental and control arms. The primary analysis is to ascertain benefit of the BRIGHT system (Coach + online education tools + online peer support) compared to usual care (control) will be between group (intervention vs control) comparison of primary and secondary outcomes using t tests (two-sided, $p<.05$). Statistical comparisons will be made at 8- and 12- months post enrolment, to determine if group differences manifest early and if they continue to improve or stabilize. This will be important in determining whether the BRIGHT system is necessary over a prolonged period (8 vs 12 months) to achieve its goals. Principles of intent-to-treat analysis will be applied. Repeated measures with mixed model analysis will be used to assess effect of group category and province with intervention at two time points. Within the intervention group, predictors of change scores between baseline and outcomes (dependent variable) will be tested to determine which children/families are more likely to be responsive to the BRIGHT system. Multivariate linear regressions will be conducted with independent variables, to include: parent readiness score, sociodemographic factors, child's functioning (Vineland), province, and engagement in the Igloo platform. The structural properties of the network (Igloo) will be analysed using UCINET [17]. Network analysis related to patterns of use of the online platform will be correlated with the outcome measures of interest in this study.

Sample size:

We will recruit 392 participants; we project a sample size of 352 based on: i) two-sided test of the null hypothesis at $\alpha=.05$, ii) $\beta=.80$, iii) 10% attrition; iv) difference of 0.3 SD.

Studies as of yet have not identified a minimal clinically important difference (MCID) for our primary outcome measure (the Family Empowerment Scale) that could be used to estimate sample size calculation. In the absence of a “clinimetric” MCID, a distribution-based methods approach is commonly applied that proposes a fraction of the pooled Standard Deviation (i.e. utilize effect size estimates). In this case, the difference of 0.3 standard deviation can be used to detect modest effects that may be clinically significant; or 0.5 SD for moderate to large effects [18, 19].

We aim to recruit a sample of 350 participants (randomized to either intervention or control group) across the four sites. This will be approximately 100 from British Columbia, 100 from Quebec, 75 from Manitoba and 75 from Nova Scotia. In order to be able to detect modest effects that may be clinically important (0.3 SD), this would require recruitment of a sample of 392, accounting for 10% attrition, for a sample of 352. Furthermore, this larger sample size would enable us to account for cluster randomization. We expect that all participants are independent, whether or not they live in any of the provinces. Nonetheless, it is conceivable that the association within provinces is slightly stronger (weak ICC=0.100) than the association between participants across provinces, due to environmental context (i.e. different health care and social service systems). A sample size of 346 (recruit 384, 10% attrition) would allow us to account for cluster randomization. We will apply a linear mixed model to account for the possible effect of province on the benefits of treatment on empowerment and parent competency.

PLANS FOR KNOWLEDGE TRANSLATION

The results of this study will be relevant to families, health service administrators, policy makers and providers.

Families: Families will be important consumers of the results of this study. In order to determine how best to communicate the results to them, a focus group of families will be brought together. They will guide strategy and tactics with respect to the study results. The content for this knowledge translation will be particularly focussed on the benefits and challenges from the perspective of families. With respect to tactics, it is anticipated that family councils, childhood-disability focussed organizations, the media, family-guided web-based materials and providers will be modalities undertaken to reach families. This plan will be modified subsequent to the focus group with families after the conclusion of the study.

Policy-makers and health/social service administrators: This audience will be a critical audience given the wait-lists and waiting times for developmental services that parents experience. The content for this audience will focus on the nature of the intervention, the key ingredients that showed success, the cost-utility analysis. With respect to tactics, a policy dialogue will be hosted in year 5 and policy options for implementation will be constructed. A policy paper with associated briefing notes (generic), which can be tailored to each province and their relevant ministries, will be created.

Providers: Providers will be interested in these results. The focus with respect to content for this audience is on the effectiveness of the intervention and its relation to “usual care”. Tactics will include peer-reviewed articles and presentation at local, provincial, and national meetings will be undertaken.

PLANS FOR TRAINING

The British Columbia and Quebec recruitment sites have funding to support a doctoral or postdoctoral trainee throughout the duration of the project. The trainees will have the opportunity to expand their knowledge and expertise in health services research, network analyses, family engagement and pragmatic randomized trials. In addition, the trainees will be expected to participate in CHILD-BRIGHT’s patient-oriented training program.

The investigators of our ‘BRIGHT Coaching system’ study will be working collaboratively with investigators from other projects (theme 3 projects, Strongest Families in theme 2) that are applying a coach model to develop a manual. This handbook will describe health coach frameworks and key ingredients of success (from the literature), and define the coach’s roles and responsibilities and provide case examples to further clarify this service delivery approach. Our team will work with the other teams to develop training modules on the coach model, for the benefit of particular stakeholder groups that would be interested in learning more about this model of care. These modules will be tailored to the user (i.e. parents, clinicians, policymakers and health administrators) to promote greater understanding of the benefits and challenges. There will be an interactive component to enable stakeholders across groups to discuss the potential applications of a coach model to support children with disabilities and their families across key transition points of care.

IMPLICATIONS FOR CHILD AND FAMILY WELL BEING - PRACTICE AND POLICY

The preschool years between 3 and 6 years of age are a time of great developmental change and a time of great concern for parents who see differences in their child’s development. Coordination of services, for those children receiving them can be challenging and confusing. Waiting for services for those not yet

receiving them can lead to frustration and fear. From a policy and health/social system administrator perspective, despite large investments, waiting lists often exist.

At the conclusion of this study, should the hypotheses be proven to be correct, the following impact will be seen for the following groups:

- *Families:* This study will produce an evidence-based mechanism to support families during times of uncertainty. It will be effective across developmental severity levels making it very generalizable. It will enable families in feeling supported, will enhance family empowerment, will support enhanced family well-being. With guidance regarding services, it is expected that there will be reduced travel time and time off work for families, thereby reducing costs to families.
- *Policy makers and health administrators:* The results and KT products will provide mechanisms to facilitate discussion regarding how the program is delivered regionally. It is anticipated that the program and its key ingredients could be delivered through multiple means, allowing governments to tailor its use to reflect their provincial, regional and local nuances.
- *Service Delivery/Developmental Programs:* The draw on services across provinces will be reduced as families receive information that prevents them from being in the incorrect queue for services and assists them in coordinating their own services as has been done with other self-management programs in adults with chronic disease. Rural and remote service delivery will be enhanced through this care, which can be delivered from a distance.

TABLE 1. MILESTONES, DELIVERABLES

Major Project Activities/ Milestones	Year 1 (M)ilestones	Year 2 (M)ilestones	Year 3 (M)ilestones/ (D)eliverable	Year 4 (M)ilestones/ (D)eliverable	Year 5 (M)ilestones/ (D)eliverable
Clinical study protocol and ethics review	(D) Protocol finalized with family input (D) Ethics approves finalized protocol across sites				
Clinical procedures – Coaching intervention	(M) Families actively engaged in development of coaching intervention (M) Coaching procedures co-developed across relevant CHILD-BRIGHT projects (D) Coaching procedure finalized and manualized	(M) Coaching intervention pilot study for feasibility (D) Revised coaching manual post- pilot	(M) Coaching intervention being utilized	(M) Coaching intervention used and ceased with end of study period	(D) Coaching intervention results analyzed and presented
Recruitment	(M) Recruitment strategy plan for each site	(M) Recruitment strategy piloted	(M) Recruitment strategy used (D) Recruitment completed		
Educational tools	(M) Families and health providers collaborate to confirm foci for educational tools (D) Educational tools for e-health platform curated	(M) Educational tools on online education platform piloted in pilot study (M) Revisions to educational tools made based on pilot	(M) Online education tools used in intervention	(M) Online education tools used and use ceased at end of study period	(D) Evaluation of value of tools completed
Igloo online platform	(M) Families and health providers engaged with	(M) Customized platform trialed among parent	(M) Platform utilized by study sample		(D) Evaluation of value of

	customizing platform	advisory group, and potentially in pilot (D) Igloo platform finalized			platform completed
Data collection, measures and analysis	(M) Finalize tools and measures to be used with family engagement	(M) Baseline measures piloted	(M) Baseline and 8-month measures (child, family, network) collected	(M) 12-month measures collected and (D) completed (M) Plan network analysis	(M) Qualitative interviews completed (D) Analysis of all data in relation to hypotheses (D) Network analysis completed
Knowledge translation				(M) Scale up work with families regarding KT (M) Plan interactions with policy makers regarding KT (M) Project plan regarding clinicians and KT	(D) Carry out KT plan with families (D) Hold KT forum and complete policy briefs for policy makers (D) Complete clinician documents (D) Manuscripts complete

Anticipated Outcomes:	
 • Parents will be more empowered and knowledgeable, and make more informed decisions about their child's care and development • Services accessed will be appropriate based on the child's and family's needs and developmental services will be more cost-effective • Providers will feel confident that their clients are receiving appropriate services and supports based on client needs
Anticipated Impacts:	
A more responsive health care system that meets the developmental needs of children and the health and knowledge needs of parents.
 
The electronic platform (Igloo) will be tested with respect to its utility as an information and support network, for consideration for other chronic diseases of childhood.

	Research trainees will be well prepared to pursue future child health research with a strong inclusion of families and their support networks.
--	--

TABLE 2. SUMMARY OF MAIN PREDICTOR AND OUTCOME MEASURES

VARIABLES	MEASURE
PRIMARY PREDICTOR	
Intervention versus control group	Randomization to one group
Other Key Variables	
Child's age	Age at recruitment in months to one decimal place
Child's sex	Male/female
Parental involvement in the intervention	Mother vs father; # of uses of Igloo platform (areas: coach, online education tools, peer support)
Socioeconomic factors	Parents' education level, postal code
Readiness for health coach model	Readiness for coaching questionnaire (3-points)

OUTCOMES	
PRIMARY	
Empowerment (ability to manage and take charge) at the family, services and community levels	Family Empowerment Scale
Parental satisfaction and efficacy with competency	Parents Sense of Competence Scale
SECONDARY	
Family stress level	Parenting Stress Index
Parental well-being (quality of life)	SF-36
Family-centered care provided by coach to include educational benefits	Measure of Process of Care

Health service utilization and costs	Resource Utilization Questionnaire (adapted from [name] and [name])
Profile Form	Surveys on background of participant & family structure
Demographic Form	Survey on family socioeconomic status and education level
Child's functional abilities	Vineland
Survey on parent/caregiver mental health	Parenting Morale Index

REFERENCES

1. Majnemer, A., et al., *A new look at outcomes of infants with congenital heart disease*. Pediatric neurology, 2009. **40**(3): p. 197-204.

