Recruitment will begin with family contact. Each site manages their own recruitment process and protocol. Please see our *Recruitment Protocol* in Montreal (Appendix). Families will be contacted via the centre to which they were referred for developmental diagnosis and assessment. A member of the clinical team will ask if they are interested to learn more about the BRIGHT Coaching study. If interested, the families' contact information will be shared with the local research assistant (RA) overseeing the trial. The RA will speak to a parent by phone and follow up with an introductory letter by mail and/or email explaining the procedures of the study, together with the consent form. After 1 to 10 days, the RA will call the family to determine interest in participating and answer any questions. If interested in participating, parent can either 1) sign the consent form and scan by email to the RA, 2) send the consent form to the RA by mail/ hand it to them in person, 3) agree to a verbal consent process and verbal consent will be given to the RA over the phone (in accordance with the Tri-Council Policy Statement on verbal consent). Once consent is signed, participants will conduct baseline assessments including documentation of their care and social networks, and be randomized using a computer-generated algorithm; randomization will be stratified by site. The allocation ratio for intervention or control will be 1:1 for each site.

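### The primary analysis is an unadjusted t test although baseline scores and the stratification factor, site, are collected; it is valid, but adjusting would add power at no cost

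*Protocol*

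**What the plan says.** Under Statistical analyses, the protocol names the primary analysis of benefit as a "between group (intervention vs control) comparison of primary and secondary outcomes using t tests" (two-sided, 5% level), and adds that "Statistical comparisons will be made at 8- and 12- months post enrolment". It does not say whether the tests use follow-up scores or changes from baseline.

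The covariates are available:

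- **Baseline scores.** The section on data collection and outcome measures states that "Outcome measures will be measured at baseline, 8 months post-entry and 12 months post-entry". Table 1 lists the same under year 3: "Baseline and 8-month measures (child, family, network) collected".
- **Site.** Under Study procedures, "randomization will be stratified by site", with 1:1 allocation within each site.

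Other models are planned. Statistical analyses mentions a repeated-measures mixed model for group and province. Sample size says "We will apply a linear mixed model to account for the possible effect of province on the benefits of treatment", for empowerment and parent competency. Neither is called primary and neither names the baseline score. Change from baseline appears only in regressions within the intervention arm, which do not compare arms.

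**The concern.** A participant's baseline score usually predicts the same score 8 or 12 months later. An analysis that ignores it leaves that predictable variation in the error term. Likewise, if outcomes differ between sites, leaving out the stratification factor keeps between-site variation in the standard error, although stratified allocation has already balanced it between arms.

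Three things are at stake:

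- **Power.** The sample size has no margin: 352 is the smallest even total that reaches 80% with a t test. The protocol also gives a recruitment target of 350, at which power falls short.
- **Chance imbalance.** A t test on follow-up scores carries any baseline difference between arms into the estimate. Outcomes here are mainly self-reported and unblinded, so a visible imbalance would invite challenge.
- **An open choice of score.** If the t tests were run on change scores, power could be well below the stated figure.

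**Working it through.** **Inputs from the protocol.** Two-sided alpha 0.05; power 0.80 (written as beta, but only power 0.80 reproduces the total); difference 0.3 SD; 10% attrition; 1:1 allocation; ICC 0.100 for province; 352 analysed from 392 recruited, and elsewhere 350 recruited, so 350 × 0.9 = 315 analysed.

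**Assumed.** The correlation r between baseline and follow-up is not given, so 0.2 to 0.6 is shown. The SD is taken as equal at both times.

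**1. The plan's own figure.** A two-sample t test with d = 0.3 needs 175.4 per arm, so 176, or 352 in total. Then 352/0.9 = 391.1, so 392. Both match "this would require recruitment of a sample of 392, accounting for 10% attrition, for a sample of 352". The stated size is that of an unadjusted t test on follow-up scores, with power 80.1% at 352 and 75.6% at 315.

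**2. Baseline adjustment.** The residual SD falls to √(1 − r²), so the standardised effect becomes 0.3/√(1 − r²), at the cost of one degree of freedom. At r = 0.5 this is 0.3/0.866 = 0.346.

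**3. Change scores.** The SD of the change is √(2(1 − r)), so the effect is 0.3/√(2(1 − r)). This equals 0.3 at r = 0.5 and is smaller below it.

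Noncentral t gives:

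| r | Adjusted, 352 | Adjusted, 315 | Change score, 352 | Total for 80%, adjusted |
|---|---|---|---|---|
| 0.2 | 81.7% | 77.3% | 60.2% | 338 |
| 0.3 | 83.7% | 79.5% | 66.0% | 320 |
| 0.4 | 86.5% | 82.5% | 72.6% | 296 |
| 0.5 | 90.0% | 86.5% | 80.1% | 264 |
| 0.6 | 93.9% | 91.3% | 88.1% | 226 |

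The comparator for the last column is 352 with the follow-up t test. Adjustment beats the follow-up and change-score t tests at every r shown.

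**4. Chance imbalance.** The standard error of the baseline mean difference is √(4/352) = 0.107 SD. The chance of a difference above 0.1 SD in either direction is P(|Z| > 0.1/0.107) = 34.8%. The follow-up t-test estimate shifts by r × imbalance: at r = 0.5, 0.5 × 0.1 = 0.05 SD, one sixth of the 0.3 SD target.

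**5. Site.** Simulation with 60,000 runs, four sites in the ratio 100:100:75:75, 1:1 within site, total SD 1, no baseline covariate:

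| ICC | Analysed | Power, t test | Power, site in model | Type I error, t test | Type I error, site in model |
|---|---|---|---|---|---|
| 0.10 | 352 | 82.1% | 84.1% | 4.1% | 4.9% |
| 0.10 | 315 | 77.7% | 80.0% | 4.3% | 5.1% |
| 0.05 | 352 | 81.2% | 82.2% | 4.5% | 4.9% |
| 0.05 | 315 | 76.6% | 77.8% | 4.5% | 4.9% |
| 0 | 352 | 80.0% | 80.0% | not shown | not shown |
| 0 | 315 | 75.3% | 75.2% | not shown | not shown |

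The t test is slightly conservative when sites differ. Putting site in the model costs nothing visible when they do not.

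**6. Both together.** In a separate simulation of 20,000 runs at 352 analysed, ICC 0.10 and r = 0.5, power was 81.8% for the t test and 92.5% with baseline and site in the model. The adjusted model's type I error was 5.0% in 60,000 runs.

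**The case against.** The t test is valid and matches its own sample-size calculation, and covariate lists are often left to the SAP. Both statements are true. But the protocol does not leave the matter open: it names the primary test, and that test cannot take a covariate.

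The planned mixed models already bring in province, and with four sites in four provinces this largely covers site. That stands in part. The site gain is small in any case, and nil under the protocol's own expectation: "We expect that all participants are independent, whether or not they live in any of the provinces". The models are not primary, however, and the baseline gap remains.

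The gain rests on an assumed correlation. This stands: at r = 0.2 it is under 2 points with 352 analysed.

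The change-score figures describe an analysis that the protocol does not state, and follow-up scores are the more natural reading because 352 is their sample size. This also stands, so those figures are conditional and do not describe the plan.

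Chance imbalance is not bias, and the t test's standard error already allows for it. Correct: it is the same precision gain seen from another side and should not be counted twice.

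A linear model may suit cost data poorly. That is fair, but the protocol already plans t tests on those outcomes, which is no better.

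**Conclusion.** The point holds as a worthwhile improvement and not as an error. With 352 analysed, the stated 80% power is met without adjustment.

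Baseline adjustment would add roughly 2 to 14 percentage points at 352 analysed, for r from 0.2 to 0.6. Put another way, 80% power would need 338 down to 226 participants in place of 352. With 315 analysed, it brings power back above 80% at r = 0.4 and just misses at r = 0.3. These figures assume equal SDs at baseline and follow-up, and a correlation that the protocol does not supply.

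Site contributes about 2 points at an ICC of 0.10, about 1 at 0.05, and none under independence. The baseline score is therefore the main gap.

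**What to change.** Make the primary between-arm analysis a linear mixed model of the 8- and 12-month scores. Its fixed effects should be treatment, visit, treatment by visit, baseline score and site (province), and it should allow for correlation between a participant's two visits. Report the treatment difference with its 95% confidence interval at each visit. This amounts to promoting the mixed model already planned and adding the baseline score.

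Use the same model for the other continuous outcomes measured at baseline. Keep the t tests as a sensitivity analysis and state whether they use follow-up or change scores. Keep the question of whether benefit differs by province as a separate treatment-by-province analysis.

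The cost is analysis wording only, with no new data and no extra families. The change does not settle the conflict between 350 and 392 recruited or the choice of a single primary time point; both need their own decision.
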